### Hematology

A complete blood count will include:

Hematocrit	Hemoglobin
Red blood cell count	White blood cell count and differential [1]
Neutrophils	Granulocytes
Lymphocytes	Platelets
Eosinophils	Basophils
Monocytes	

1. Manual microscopic review is performed only if white blood cell count and/or differential values are out of reference range.

### Pregnancy Testing

For female subjects of childbearing potential, a urine pregnancy test is acceptable at any visit that warrants a pregnancy test.

## Statistical Analysis Plan Template

Sponsor:	ProQR Therapeutics		
Protocol:	PQ-110-002		
Document Version No.:	1.0	Document Date:	04 JAN 2022

---

## Statistical Analysis Plan Template

Sponsor:	ProQR Therapeutics		
Protocol:	PQ-110-002		
Document Version No.:	1.0	Document Date:	04 JAN 2022

---

## Statistical Analysis Plan Template

Sponsor:	ProQR Therapeutics		
Protocol:	PQ-110-002		
Document Version No.:	1.0	Document Date:	04 JAN 2022

## Statistical Analysis Plan Template

Sponsor:	ProQR Therapeutics		
Protocol:	PQ-110-002		
Document Version No.:	1.0	Document Date:	04 JAN 2022

---

## Statistical Analysis Plan Template

Sponsor:	ProQR Therapeutics		
Protocol:	PQ-110-002		
Document Version No.:	1.0	Document Date:	04 JAN 2022

---

### ABBREVIATIONS

Abbreviation	Definition
$\lambda_z$	elimination rate constant
AE	adverse event
ALP	alkaline phosphatase
ALT	alanine aminotransferase
AON	antisense oligonucleotide
AREDS	age-related eye diseases study
ARLNS	age-related eye diseases study clinical lens grading system
AST	aspartate aminotransferase
$AUC_{0-\infty}$	area under the curve 0 hour to infinity
$AUC_{0-t_{last}}$	area under the curve 0 hour to time of the last measurable concentration
BCVA	Best Corrected Visual Acuity
BRVT	Berkeley Rudimentary Vision Test
BUN	blood urea nitrogen
CEP290	Centrosomal Protein of 290 kDa
CEP290	CEP290 gene
CF	counting fingers
CKD-EPI	Chronic Kidney Disease Epidemiology Collaboration
CL	clearance
$C_{last}$	last observed concentration
$C_{max}$	maximum concentration
$C_0$	trough value
CSR	clinical study report
CVAQC	Cardiff Visual Ability Questionnaire for Children
EC	Ethics Committee
ECG	electrocardiogram
eCRF	electronic case report form
eGFR	estimated glomerular filtration rate
EOS	end of study
ERG	electroretinogram

## Statistical Analysis Plan Template

Sponsor:	ProQR Therapeutics		
Protocol:	PQ-110-002		
Document Version No.:	1.0	Document Date:	04 JAN 2022

Abbreviation	Definition
ETDRS	Early Treatment Diabetic Retinopathy Study
FST	Full-field Stimulus Testing (also, Full-field Stimulus Threshold Testing or Full-field Scotopic Threshold Testing)
HM	hand motion
ICH	International Council on Harmonisation
INR	international normalized ratio
IOP	intraocular pressure
IVT	intravitreal
LCA	Leber's congenital amaurosis
LDH	lactic dehydrogenase
LLOQ	lower limit of quantification
LogMAR	Logarithm of the Minimum Angle of Resolution
LP	light perception
MedDRA	Medical Dictionary for Regulatory Activities
NIH	National Institute of Health
NIRAF	near infrared autofluorescence
OCI	oculomotor instability
OCT	optical coherence tomography
ONL	outer nuclear layer
p.Cys998X	Protein product from the c.2991+1655A>G mutation in the CEP290 gene
PK	pharmacokinetic
PLR	pupillary light reflex
PRO	patient reported outcome
PT	preferred term
SAE	serious adverse event
SEM	standard error of mean
SAP	statistical analysis plan
SOC	system organ class
SOE	schedule of events
SUN	Standardization of Uveitis Nomenclature

## Statistical Analysis Plan Template

Sponsor:	ProQR Therapeutics		
Protocol:	PQ-110-002		
Document Version No.:	1.0	Document Date:	04 JAN 2022

---

Abbreviation	Definition
SUSAR	suspected unexpected serious adverse reaction
TEAE	treatment-emergent adverse event
T 1/2	terminal half-life
T max	time of maximum concentration
ULN	upper limit of normal
US	United States
V d	volume of distribution
VF	visual field
VFQ-25	Visual Function Questionnaire-25
WOCBP	women of childbearing potential

## Statistical Analysis Plan Template

Sponsor:	ProQR Therapeutics		
Protocol:	PQ-110-002		
Document Version No.:	1.0	Document Date:	04 JAN 2022

---

### 1. INTRODUCTION AND OBJECTIVES OF ANALYSIS

#### 1.1. Introduction

ProQR Therapeutics (ProQR) is developing an antisense oligonucleotide (AON) product, sepofarsen, for the treatment of patients with Leber congenital amaurosis (LCA) due to the c.2991+1655A>G (p.Cys998X) mutation in the Centrosomal Protein of 290kDa (CEP290) gene. Leber congenital amaurosis caused by mutations in the *CEP290* gene (ie, LCA type 10 [LCA10]) is a severe inherited retinal degenerative disease resulting in blindness, often in early childhood. There are currently no approved therapies for the treatment of LCA10 due to the c.2991 +1655A>G mutation and an important unmet medical need exists. The primary goal of the development plan for sepofarsen is to provide a treatment to overcome the genetic defect in patients with at least 1 *CEP290* allele containing the *CEP290* mutation, resulting in functional vision restoration or preservation. The intended route of administration is intravitreal (IVT) injection.

PQ-110-002 study is an open-label, extension study from study PQ-110-001, to evaluate the safety, tolerability, efficacy, and pharmacokinetics of sepofarsen in subjects with LCA due to c.2991+1655A>G mutation in the *CEP290* gene. PQ-110-001 was a 1b/2 phase, open-label, multiple dose, dose escalation study to evaluate the safety and tolerability of sepofarsen in subjects with LCA due to the above mentioned mutation.

#### 1.2. Objectives of Statistical Analysis

This statistical analysis plan (SAP) describes the populations for analysis, data handling rules, statistical methods, and formats for data presentation that will be required for the analysis of data from trial PQ-110-002. The statistical analyses and summary tabulations that will be produced for the analysis as described in this SAP will provide the basis for the results sections of the interim and final clinical study

## Statistical Analysis Plan Template

Sponsor:	ProQR Therapeutics		
Protocol:	PQ-110-002		
Document Version No.:	1.0	Document Date:	04 JAN 2022

---

reports (CSRs) for this trial. The SAP will also outline any differences between the currently planned analyses and those specified in the clinical study protocol.

## Statistical Analysis Plan Template

Sponsor:	ProQR Therapeutics		
Protocol:	PQ-110-002		
Document Version No.:	1.0	Document Date:	04 JAN 2022

## 2. STUDY DESIGN

### 2.1. Synopsis of Study Design

This study is an open-label, extension study to evaluate the safety, tolerability, efficacy, and pharmacokinetics of sepofarsen in subjects with LCA due to c.2991 +1655A>G mutation in the *CEP290* gene.

Subjects will be given the opportunity to enroll into this extension study for continued dosing if available data support current and/or future benefits for the subject. The Investigator, in consultation and agreement with the Medical Monitor, will decide on enrollment of each individual subject, as well as on dosing of the first treated eye and treatment initiation of the contralateral eye. Continued subject treatment in this study is desirable, but cannot be guaranteed, since it will depend on the risks and benefit of further treatment on a case-by-case basis, as discussed and agreed upon with the Medical Monitor.

Dose modifications or modifications of the dosing interval will be considered on the basis of emerging safety and/or efficacy data and if it is anticipated to be in the best interest of the subject.

The contralateral eye and the first treated eye will be injected 3 months apart. The injection interval of 3 months between both eyes will limit burden for the subjects. This between-eye interval could be adapted if safety data are supportive, and for logistic reasons, and in agreement with the Medical Monitor. The same safety monitoring protocol and efficacy assessments will apply to both eyes.

### 2.2. Randomization Methodology

This is an open-label study; randomization is not required as the study is not randomized.

### 2.3. Stopping Rules and

The Investigator or the Medical Monitor may stop treatment for an individual subject due to an

## Statistical Analysis Plan Template

Sponsor:	ProQR Therapeutics		
Protocol:	PQ-110-002		
Document Version No.:	1.0	Document Date:	04 JAN 2022

---

AE. The severity of the event(s), as well as the temporal relationship to study drug administration, potential for worsening of the event(s) with continued sepofarsen and association with other safety signals or laboratory values should be considered in the decision to stop treatment. The Medical Monitor must be notified of any subject who stops treatment due to an AE. Adverse events considered to be related to the study drug should be taken into account in the benefit/risk assessment.

Subjects who discontinue study drug will be encouraged to remain in the study for observation for at least 3 months post last dose.

The Investigator and/or the Sponsor may decide to stop treatment for an individual subject due to an AE.

This is an open-label study; masking is not required.

## Statistical Analysis Plan Template

Sponsor:	ProQR Therapeutics		
Protocol:	PQ-110-002		
Document Version No.:	1.0	Document Date:	04 JAN 2022

---

### 2.4. Study Procedures

The schedule of assessments, as outlined in the study protocol, is provided in

## Statistical Analysis Plan Template

Sponsor:	ProQR Therapeutics		
Protocol:	PQ-110-002		
Document Version No.:	1.0	Document Date:	04 JAN 2022

---

## Statistical Analysis Plan Template

Sponsor:	ProQR Therapeutics		
Protocol:	PQ-110-002		
Document Version No.:	1.0	Document Date:	04 JAN 2022

## Statistical Analysis Plan Template

Sponsor:	ProQR Therapeutics		
Protocol:	PQ-110-002		
Document Version No.:	1.0	Document Date:	04 JAN 2022

## Statistical Analysis Plan Template

Sponsor:	ProQR Therapeutics		
Protocol:	PQ-110-002		
Document Version No.:	1.0	Document Date:	04 JAN 2022

---

## Statistical Analysis Plan Template

Sponsor:	ProQR Therapeutics		
Protocol:	PQ-110-002		
Document Version No.:	1.0	Document Date:	04 JAN 2022

### 2.5. Safety, Efficacy and Pharmacokinetic Endpoints

#### 2.5.1. Safety Endpoints

##### 2.5.1.1. Primary Endpoint

The primary endpoints are:

- Frequency and severity of ocular AEs
- Frequency and severity of non-ocular AEs

#### 2.5.2. Efficacy Endpoints

##### 2.5.2.1. Secondary Endpoints

Secondary endpoints include:

- Change from baseline in BCVA
- Change from baseline in Mobility course score (unilateral and binocular)
- Change from baseline in photoreceptor outer segment layer thickness by optical coherence tomography (OCT) (if applicable)
- Change from baseline in OCI
- Change from baseline in Full-FST (blue and red stimuli; white at Investigator discretion) (thresholds)
- Change from baseline in PROs as measured by:
  - Visual Function Questionnaire-25 (VFQ-25) score (adult subjects), or
  - Cardiff Visual Ability Questionnaire for Children (CVAQC) score (pediatric subjects)
- Change from baseline in Pupillary Light Reflex (PLR) (latency and amplitude)

## Statistical Analysis Plan Template

Sponsor:	ProQR Therapeutics		
Protocol:	PQ-110-002		
Document Version No.:	1.0	Document Date:	04 JAN 2022

- Change from baseline in Near Infrared AutoFluorescence (NIRAF)
- Pharmacokinetics: Characterize the PK profile of sepofarsen in serum

### 2.5.2.2. Exploratory Endpoints (at Investigator Discretion)

### 2.5.3. Pharmacokinetic Endpoints

It is expected that the vast majority of measured PK concentrations is below limit of quantification (BLQ). Thus, no pharmacokinetic parameters ( $C_{max}$ ,  $T_{max}$ ,  $AUC_{0-24}$ ,  $AUC_{last}$  and  $AUC_{0-inf}$ ) will be derived. All individual measurement results above limit of quantification will be shown in a individual level table, and all measurements – above or below limit of quantification will be presented in the listings.

## Statistical Analysis Plan Template

Sponsor:	ProQR Therapeutics		
Protocol:	PQ-110-002		
Document Version No.:	1.0	Document Date:	04 JAN 2022

### 3. SUBJECT POPULATIONS

#### 3.1. Population Definitions

The following subject populations will be evaluated and used for presentation and analysis of the data:

- **All Screened Subjects:** All subjects who provided informed consent or assent document to participate in the study.
- **Safety Population:** All subjects who received any sepofarsen during study PQ-110-001 and were enrolled in this study.-
- **Efficacy Evaluable Population:** All subjects who received any sepofarsen with at least one baseline 002 and post-baseline 002 BCVA measurement.
- **Per Protocol Analysis Set:** All subjects in the Efficacy Evaluable Population, with the exception of subjects and/or data points with major protocol deviations affecting subjects and/or specific assessments within a subject (see Section 3.2). The list of major protocol deviations selected for exclusion from this analysis set will be completed prior to database lock.

The Safety Population is the primary population for the summaries of demographics, baseline disease characteristics, medical history, concomitant medications, major protocol deviations and all safety endpoints. The Efficacy Evaluable Population is the primary population for the analyses of all efficacy endpoints, where missing values will be reported for subjects that have missing values in their baseline measurements of that specific secondary endpoint. A subset of efficacy endpoints may be evaluated for the Per Protocol Population.

Unless otherwise stated, data presentations will be listed and summarized by treatment group.

## Statistical Analysis Plan Template

Sponsor:	ProQR Therapeutics		
Protocol:	PQ-110-002		
Document Version No.:	1.0	Document Date:	04 JAN 2022

### 3.2. Protocol Deviations

Departures from the protocol will be classified as major or minor protocol deviations. The list of major protocol deviations, including those to be excluded from the per protocol analysis set, will be completed prior to database lock. The details of the protocol deviations will be described in a separate Protocol Deviation Plan.

## Statistical Analysis Plan Template

Sponsor:	ProQR Therapeutics		
Protocol:	PQ-110-002		
Document Version No.:	1.0	Document Date:	04 JAN 2022

### 4. STATISTICAL METHODS

#### 4.1. Sample Size Justification

The sample size is determined by the number of subjects completing study PQ-110-001 who meet the inclusion and exclusion criteria and provide informed consent or assent document.

#### 4.2. General Statistical Methods and Data Handling

##### 4.2.1. General Methods

All outputs will be incorporated into bookmarked PDFs and /or Microsoft Excel or Word files, sorted and labeled according to the International Conference on Harmonisation (ICH) recommendations, and formatted to the appropriate page size(s).

Tabulations will be produced for appropriate demographic, baseline, safety and efficacy parameters. For continuous efficacy variables, the data will be summarized using the number of subjects, mean, standard deviation, standard error, median, minimum, maximum and 95% confidence intervals for the mean. For all other continuous variables, the data will be summarized using the mean, standard deviation, median, minimum and maximum. All categorical variables will be summarized by the number of subjects and percentage within each category (with a category for missing data, if any) of the parameter. For any categorical variable for an efficacy endpoint, summary tabulations of the variable will also include 95% confidence intervals for the percentage.

##### 4.2.2. Treatment Groups for Analysis

Safety and efficacy data will be summarized by treatment group. The first treated eyes data will be summarized based on the treatment group allocation in study PQ-110-001. The subjects who started with 320/160 µg in study PQ-110-001 will be moved to 160/80 ug group in study PQ-110-002; other subjects who started with 160/80 µg in study PQ-110-001 will continue the same dose in study PQ-110-002. The contralateral eyes data will be summarized for treated and non-treated for the overall study

## Statistical Analysis Plan Template

Sponsor:	ProQR Therapeutics		
Protocol:	PQ-110-002		
Document Version No.:	1.0	Document Date:	04 JAN 2022

population in study PQ-110-002.

### 4.2.3. Computing Environment

All descriptive statistical analyses will be performed using SAS statistical software (Version 9.4), unless otherwise noted. Medical History and adverse events will be coded using MedDRA Version 20.0. Concomitant medications will be coded using World Health Organization (WHO) Drug Global B3/C3-format March 1, 2021.

### 4.2.4. Definition of Baseline

For the endpoints collected on the subject level, the screening visit value in study PQ-110-002 will be defined as Baseline 002 values. For the endpoints collected on the eye level, there are three types of baseline values used for study PQ-110-002:

- Baseline 001: for BCVA, it is defined as  
for mobility course and FST, the average of measurements at pre-dose in study PQ-110-001 is considered as baseline 001.
- Baseline 002: for BCVA, it is defined as  
; for mobility course and FST, it's defined as the average of last two measurements only if the interval between them is up to 1 month before entering study PQ-110-002. Otherwise the most recent value will be taken as baseline 002. For the other endpoints, the screening value in study PQ-110-002 is used as baseline 002 value.
- Pre-dose Baseline: the efficacy endpoints collected on the eye level except BCVA, mobility course and FST, the baseline 002 will be used. For BCVA, mobility course and FST, Baseline 001 values are used for the first treated eye, non-treated contralateral eye as well as both eyes. For treated contralateral eye,
  - For BCVA, the baseline result corresponds to the best of the two most recent BCVA values available before the first dose of treatment with sepofarsen in that respective eye

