#### **4.1.3 Exploratory Endpoints (at Investigator Discretion)**

## 4.2 Study Design

PQ-110-002 study is an open-label extension study to evaluate the safety, tolerability, efficacy, and pharmacokinetics of QR-110 in subjects with LCA due to c.2991+1655A>G mutation (p.Cys998X) in the *CEP290* gene.

Subjects will be given the opportunity to enroll into the extension phase study PQ-110-002 for continued dosing if available data support current and/or future benefits for the subject from QR-110 treatment. The decision will be based on the assessment of individual subject's benefit/risk based on individual data and data from QR-110 clinical studies. The Investigator, in consultation with the Medical Monitor, will decide on enrollment of each individual subject, as well as on dosing of the first treated eye and treatment initiation of the contralateral eye. Continued subject treatment in this study is desirable, but cannot be guaranteed, since it will depend on the risks and benefit of further treatment on a case-by-case basis, as discussed and agreed upon with the Medical Monitor.

Dose modifications or modifications of the dosing interval will be considered on the basis of emerging safety and/or efficacy data and if it is anticipated to be in the best interest of the subject.

The contralateral eye and the first treated eye will be injected 3 months apart. The injection interval of 3 months between both eyes allows thorough safety evaluation and will decrease subject burden, with a 3 month-visit frequency during the course of the study. This between-eye interval could be adapted if safety data are supportive, and for logistic reasons, and in agreement with the Medical Monitor. The same safety monitoring protocol and efficacy assessments will apply to both eyes.

QR-110 will be administered via IVT injection in accordance with the procedures outlined by the American Academy of Ophthalmology ([Avery 2014](#)).

A program-specific review of safety, which may include independent experts, will be in place to assess emerging data from clinical studies on an ongoing basis.

Baseline functional and structural measurements for the first treated eye will be those from study PQ-110-001. Baseline functional and structural measurements for the contralateral eye will be those from the Screening/Day 1 visit of the current study which is the last visit of study PQ-110-001 (see [Section 4.2.1.1](#)).

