#### **9.4.1 Adverse Event Reporting Period**

Any event/condition noted once the subject receives their first dose of study drug in the contralateral eye will be captured as an AE.

In the first treated eye all events/conditions will be captured as an AE as treatment continues from study PQ-110-001.

All AEs and SAEs regardless of attribution will be collected until at least 3 months following the last administration of study drug or the subject's EOS visit, whichever is later. At the last scheduled visit, the Investigator should instruct each subject to report to the Investigator any subsequent AEs/SAEs that the subject's personal physician believes could be related to prior study treatment.

Adverse events and SAEs related to study drug that persist > 3 months after the last study drug dose should be followed until resolution or until they return to baseline, stabilize, the subject is lost to follow-up, or it has been determined that the study drug or participation is not the cause of the AE/SAE.

Resolution of AEs and SAEs (with dates) should be documented on the AE eCRF and SAE form (if applicable) and in the subject's medical record to facilitate source data verification.

For some SAEs, the Sponsor or its designee may follow-up by telephone, facsimile, electronic mail, and/or a monitoring visit to obtain additional case details deemed necessary to appropriately evaluate the SAE report (eg, hospital discharge summary, consultant report, or autopsy report).

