## **10.0 STATISTICAL METHODOLOGY**

### **10.1 General Considerations**

Analyses will generally be descriptive in nature and will focus on data collected during this study. Baseline functional and structural measurements for the first treated eye will be those from study PQ-110-001. Baseline functional and structural measurements for the contralateral eye will be collected during the Screening visit. The incidence of AEs and changes in clinical laboratory assessments will be summarized for subjects by dose group, age category (pediatrics and adults), and for the study population. Efficacy endpoints will be summarized for all subjects using descriptive statistics for each eye. For all the relevant analyses, the data may be summarized for subjects by dose group, age category, genetic status, and severity of disease (BCVA and other visual function and/or functional vision parameters). An analysis by 3- or 6-month intervals may also be performed. Summary statistics for other safety, efficacy, and PK endpoints will be presented. Further details will be provided in the Statistical Analysis Plan (SAP).

A comprehensive SAP will specify the statistical methodology, and table, listing, and figure (TLF) formats for all aspects of the planned analyses. The SAP supports the completion of the Clinical Study Report (CSR) for this protocol.

All AEs will be considered in determining the safety profile of QR-110 unless obviously unrelated. As an open-label extension study, exploratory analyses not necessarily identified in the SAP may be performed to support the clinical development program. Any p values that will be calculated according to the analysis plan will be interpreted in view of the exploratory nature of the study. Additionally, no adjustment for multiplicity will be done due to the exploratory nature of the study. Any post-hoc, or unplanned, analyses not identified in the SAP will be clearly identified in the CSR, in accordance with applicable Standard Operating Procedures (SOPs) of the Sponsor.

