### **10.4 Subject Disposition, Demographics and Baseline Disease Characteristics**

Subject disposition will be summarized for the safety population by dose group and age. The number and percentage of subjects enrolled in each study center will be presented by geographic region (North America and Europe).

The number and percentage of subjects who receive QR-110 will be tabulated by the number of doses and the QR-110 dose group.

Subject demographics and baseline characteristics will be summarized for each dose group, age, and for all subjects combined. Subject characteristics at baseline include age, race, body weight, and height. Baseline disease characteristics include ophthalmic examinations, measurements and tests, as previously described. Baseline data is defined as the data most recently collected and/or the measure reflecting the highest level of visual function (eg, for ophthalmic assessments performed two or more times) prior to the first dose of study drug in this or study PQ-110-001.

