## Statistical Analysis Plan Template

Sponsor:	ProQR Therapeutics		
Protocol:	PQ-110-002		
Document Version No.:	1.0	Document Date:	04 JAN 2022

in study PQ-110-002 (in a maximum time-window of 1 month before dosing). If only one observation is available on or prior to the subject's first dose, that observation will be used as the pre-dose baseline value. For mobility course, FST and OCT, the data most recently collected prior to the subject's first dose of study treatment in study PQ-110-002 will be used as the pre-dose baseline value.

- For other efficacy endpoints collected on the eye level, the baseline 002 will be used.

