## Statistical Analysis Plan Template

Sponsor:	ProQR Therapeutics		
Protocol:	PQ-110-002		
Document Version No.:	1.0	Document Date:	04 JAN 2022

performed later or earlier than planned in the protocol. All data to be summarized over time will be tabulated by visit, based on the schedule of events.

The Screening/ Day 1 visit should be the last visit of study PQ-110-001, ie, all Screening/Day 1 assessments should take place during the EOS visit of study PQ-110-001. If these visits do not occur at the same time, a separate Screening/Day 1 visit should be performed as part of PQ-110-002. Dosing visits occur on Day 1 for the contralateral eye and then every 6 months. Dosing visits for the previously (first) treated eye will occur 3 months after the dosing visit for the contralateral eye and then every 6 months. Study center phone calls to the subjects will occur 7 days post-IVT injection,  $\pm$ 3 days. The End of Study (EOS) visit occurs 3 months after the last dose of study drug for a subject.

For each visit, a visit window will establish a time interval around which data from the scheduled visit and any unscheduled visits will be considered to determine which data within the visit window should be summarized. In general, the visit window is the scheduled visit day +/-30 days. In exceptional cases, eg. related to the significant restrictions in site activities or subject's ability to travel to sites for visits as occurring related to the COVID-19 pandemic, extensions of the visit window or alterations in the schedule of event can be approved by the Medical Monitor. Such extensions of the visit window will be documented as protocol deviations. Still, sites should make every reasonable effort to complete scheduled visits within the time windows defined in the protocol.

Actual dates and times will be used for pharmacokinetic analyses rather than nominal days and times.

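### For OCT, NIRAF, OCI and PLR, the first treated eye's Pre-dose Baseline in the SAP is a value taken after dosing in PQ-110-001, contrary to the protocol

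*SAP*

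**What the plan says.** **SAP 4.2.4 (Definition of Baseline)** defines three eye-level baselines: Baseline 001, Baseline 002 and Pre-dose Baseline.

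- For most endpoints: "Pre-dose Baseline: the efficacy endpoints collected on the eye level except BCVA, mobility course and FST, the baseline 002 will be used". Apart from BCVA, mobility course and FST, Baseline 002 is the PQ-110-002 screening value.
- For the three named exceptions: "For BCVA, mobility course and FST, Baseline 001 values are used for the first treated eye, non-treated contralateral eye as well as both eyes".
- For the treated contralateral eye, a further rule covers OCT as well: "For mobility course, FST and OCT, the data most recently collected prior to the subject's first dose of study treatment in study PQ-110-002".

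**SAP 4.2.10** fixes the timing of screening: "all Screening/Day 1 assessments should take place during the EOS visit of study PQ-110-001". If the two visits do not coincide, a separate PQ-110-002 screening visit is held.

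**Protocol 10.1** says of the first eye: "Baseline functional and structural measurements for the first treated eye will be those from study PQ-110-001". **Protocol 4.2** says of the other: "Baseline functional and structural measurements for the contralateral eye will be those from the Screening/Day 1 visit of the current study". **Protocol 10.4** has a looser general definition, under which baseline precedes the first dose "prior to the first dose of study drug in this or study PQ-110-001".

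**SAP Section 5** says that the protocol's baseline definition relating to PQ-110-001 has been changed and points to 4.2.4. It names no endpoint or eye and gives no reason.

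**The concern.** A value called pre-dose should precede treatment of the eye it describes. In the first treated eye, on OCT, NIRAF, OCI and PLR, it does not. The same label in the same eye means Baseline 001 for mobility course and FST and, subject to a qualification discussed below, for BCVA.

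The choice matters because SAP 2.5.2.1 defines these endpoints as changes from baseline, and a secondary objective (protocol 3.2) is long-term and sustained efficacy on functional and structural measures. A reader who takes the label at face value would read first-eye change on these endpoints as change since before treatment. It is change since entry to the extension.

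**Working it through.** No figure in the plan needs reproducing: there is no power calculation, and efficacy is descriptive. The check is a comparison of the text plus one identity.

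**1. Which endpoints the rule covers.** The eye-level secondary efficacy endpoints in SAP 2.5.2.1 are BCVA, mobility course, OCT, OCI, FST, PLR and NIRAF, which makes 7. SAP 4.2.4 excepts BCVA, mobility course and FST, so 7 − 3 = 4 remain: OCT, OCI, PLR and NIRAF. SAP 4.8.4 to 4.8.7 summarise all four by eye. The separate OCT rule applies to the treated contralateral eye, so the first-eye count stays at 4.

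**2. Whether Baseline 002 precedes treatment of the first eye.** Screening is the end-of-study visit of PQ-110-001 or a separate extension visit. Protocol 9.4.1 says "In the first treated eye all events/conditions will be captured as an AE as treatment continues from study PQ-110-001", and SAP 4.8.1.3 likewise describes these eyes as treated in the parent study. On either timing the value follows dosing.

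**3. What the protocol intends.** Protocol 4.2 gives the first eye its PQ-110-001 measurements and the contralateral eye the Screening/Day 1 visit, which it identifies as the last visit of PQ-110-001. If that visit also supplied the first-eye baseline, the distinction between the eyes would be empty. The wording in 10.4 is ambiguous on its own; 4.2 and 10.1 are specific to the eye.

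**4. Whether another baseline could apply.** The SAP tables do not say which baseline they use. For these endpoints in the first eye, Baseline 002 and Pre-dose Baseline are the same value, and the readable text defines no Baseline 001 for them. The redacted gaps in 4.2.4 follow the words introducing the BCVA definitions. Even if the OCT rule were applied to the first eye, it would give a value after PQ-110-001 dosing.

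**5. What the choice does to the result.** Let Y be a later value, B001 the value before first dose in PQ-110-001, B002 the extension screening value, and d = B002 − B001. Then

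Y − B002 = (Y − B001) − d.

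- If the whole of d is kept, Y − B001 = d and the reported change is d − d = 0.
- If half is kept, Y − B001 = d/2 and the reported change is d/2 − d = −d/2.

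This holds whether d is a gain or a loss. The documents give neither its size nor its sign.

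**6. Where change is reported.** SAP 4.8.7 plans mean change explicitly for PLR. For OCT, NIRAF and OCI (4.8.4 to 4.8.6), change is explicit only in the tables of individual values. Protocol 5.1 caps enrolment at 11 subjects, hence at most 11 first treated eyes.

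**The case against.** **The extension baseline is legitimate and disclosed.** Protocol 10.1 says that analyses concentrate on data from this study, change from extension entry speaks to the word sustained in the objective, and SAP Section 5 records a baseline change. It stands that change from Baseline 002 is worth reporting and that the departure is not hidden. But the same section 10.1 assigns the first eye its PQ-110-001 baseline, and a general disclosure does not make a post-dose value pre-dose.

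**BCVA may share the later clock.** SAP 4.8.1 takes the best first-eye reading at Screening as the baseline BCVA, without naming the study, and refers to 4.2.4, where the Baseline 001 and 002 definitions for BCVA are redacted. This stands. A reader might infer that the four endpoints certainly run on a different clock from BCVA in the same eye. The documents establish that contrast for mobility course and FST; for BCVA it is qualified.

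**The reach is small.** This also stands. Observed values are shown by visit, and SAP 4.6 plans Baseline 001 summaries of ophthalmic examinations, measurements and tests, so some readers could set the two side by side.

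**The contralateral eye.** A reader might infer that its baselines should be realigned too. Moving non-treated eyes to Baseline 002 would not achieve this. SAP 4.8.1.1 and 4.8.3 show all three eye types together, and for mobility course and FST Baseline 002 can be an average of two values, whereas treated contralateral eyes use the most recent one.

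**The OCT wording.** The general rule and the separate contralateral-eye rule could be better aligned, but that is a drafting matter and does not alter the first-eye point.

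**Conclusion.** The point holds. On 4 of 7 eye-level secondary efficacy endpoints, the first treated eye's Pre-dose Baseline is a post-treatment value and departs from the protocol. First-eye change on these endpoints measures maintenance during the extension, not effect from before treatment.

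It should be fixed, but its reach is limited: descriptive analyses and at most 11 eyes, with mean change explicit only for PLR. A reader might infer that the results will be biased in a known direction, or that a real benefit will be concealed. The documents do not support that, because the change during PQ-110-001 is not given and could be a gain, a loss or nothing.

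The conclusion rests on the readable text of SAP 4.2.4 and assumes that the redacted BCVA definitions contain no Baseline 001 rule for the other endpoints.

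**What to change.** 1. In SAP 4.2.4, define Baseline 001 for OCT, NIRAF, OCI and PLR as the last value before first dose in PQ-110-001, where collected, and make it the first-eye Pre-dose Baseline.
2. Keep change from Baseline 002 as a separate column, labelled as change during the extension.
3. Show unavailable Baseline 001 values as missing, with the number available.
4. Reconcile SAP 4.8.1 with 4.2.4 on which study's Screening gives the first-eye BCVA baseline, and name the baseline in every change-from-baseline table.

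Two drafting clarifications can go in at the same time: align the OCT wording in 4.2.4, and give the reason for the baseline change in Section 5.

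The cost is SAP wording and one extra set of columns, with no new data collection. The limitation is availability: the documents do not say which of the four endpoints were measured before dosing in PQ-110-001. An eye without such a value would have only its change from Baseline 002.
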